## 2 SELECTION OF SITES/CLINICIANS

As this is a pilot, the number of sites will be limited. The sponsor has overall responsibility for site and investigator selection, but the decision to include a site will be taken jointly between MRC CTU and the PHE.

### 2.1 SITE/INVESTIGATOR INCLUSION CRITERIA

For the pilot sites:

- 500 or more MSM seen per year for HIV test.
- 50 or more HIV positive participants in current follow-up
- Experience with prescribing Truvada

In addition each clinical trial site and PI must fulfil a set of basic criteria, covering PI qualifications and PI and site responsibilities and minimum resources required during the pilot. These criteria have been agreed by the PROUD Trial Management Group (TMG) and are formalised in the signed Investigator agreement,

All approvals and contracts will be in place and all site required documentation and training completed before MRC CTU will open a site to the protocol.

### 3 SELECTION OF PARTICIPANTS

There will be **no exceptions** to eligibility requirements at the time of randomisation. Questions about eligibility criteria should be addressed prior to attempting to randomise the participant.

#### 3.1 PARTICIPANT INCLUSION CRITERIA

1. Born to male gender, age 18 years or more
2. Previously attended the enrolling clinic on at least one occasion
3. Completed a screen for HIV and STIs
4. HIV negative by a routinely used assay within 4 weeks prior to or on the day of randomisation
5. Reported unprotected anal intercourse (UAI) on more than one occasion within the 90 days prior to randomisation
6. Likely, in the opinion of the volunteer, to have UAI in the next 90 days
7. Willing and able to comply with the visit schedule throughout the follow-up period
8. Willing and able to provide written informed consent

#### 3.2 PARTICIPANT EXCLUSION CRITERIA

1. An acute viral illness that could be due to HIV seroconversion
2. Any contraindications to Truvada according to the current package insert
3. Treatment for hepatitis B infection indicated or ongoing
4. Unlikely, in the opinion of the clinician, to comply with the randomised allocation

#### 3.3 NUMBER OF PARTICIPANTS

500

#### 3.4 CO-ENROLMENT GUIDELINES

Participants cannot enrol in this study more than once.

Participation in other studies may be permitted but this must first be discussed with the MRC CTU.

Participants with confirmed HIV seroconversion (i.e. have fulfilled the primary endpoint) may enrol in other studies.

#### 3.5 SCREENING PROCEDURES & PRE-RANDOMISATION INVESTIGATIONS

Routine data will provide the information required prior to the randomisation visit.

Written informed consent to enter into the trial and be randomised must be obtained from participants after explanation of the aims, methods, benefits and potential hazards of the trial and before any trial-specific procedures are performed (see Sample Consent Form - **Appendix II**).

Signed consent forms must be kept by the investigator and documented in the CRF and a copy given to the participant. With consent, a letter should be sent to the general practitioner (GP) informing him/her of the trial and the participant's involvement in it (see **Appendix III**).

## 4 RANDOMISATION

### 4.1 RANDOMISATION PRACTICALITIES

The randomisation method is described in Section 9.1.

#### **RANDOMISATIONS**

Follow the Working Instructions to access the website

Or

Call or fax MRC CTU, Monday to Friday 08:30 to 17:00

[contact] or [contact]

A manual randomisation process will be set up to cover any instances when the electronic system is not working. This will be detailed in the trial Working Instructions.

### 4.2 PARTICIPANTS WITH REGULAR SEXUAL PARTNERS

Volunteers whose regular sexual partner is also HIV negative, will be encouraged to enrol together, and the randomisation will be managed to ensure that they are allocated to the same group to minimise the possibility of drug-sharing, and to facilitate mutual support to remain HIV negative.

## 5 TREATMENT OF PARTICIPANTS

### 5.1 INTERVENTION

The drug to be used in this trial is Truvada, which is licensed for the treatment of HIV infection in Europe and is widely used. This once daily film-coated tablet contains 245mg of tenofovir disoproxil (TDF) and 200mg of emtricitabine (FTC), both of which are nucleot/side analogue HIV-1 reverse transcriptase inhibitors. It should be taken orally with or without food. The most common adverse reactions in HIV positive individuals taking Truvada as part of combination therapy, occurring in 10% or more, are diarrhoea, nausea, fatigue, headache, dizziness, depression, insomnia, abnormal dreams and rash. Further information on Truvada in HIV positive individuals is available in the SmPC.

The investigational medicinal product (IMP), Truvada, will be manufactured and supplied by Gilead Sciences, Inc from clinical trial supply. It will be labelled for clinical trial use with MHRA approved Annex 13 compliant labels. The Truvada supplied is identical in composition to the commercially supplied Truvada used in HIV clinics across the UK. If circumstances arise that require dispensing of Truvada from normal clinic stocks this is allowed as long as this is documented appropriately.

### 5.2 TREATMENT PROCEDURES

Those allocated to an IMMEDIATE offer of Truvada on the day of randomisation will continue to have access to the drug for the duration of the study.

Those allocated to a DEFERRED offer will have access to Truvada from 12 months after enrolment, or earlier on the recommendation of the Trial Steering Committee.

#### 5.2.1 TREATMENT SCHEDULE

The treatment schedule is a once daily regimen.

#### 5.2.2 DISPENSING

The Principal Investigator will ensure that Truvada is dispensed in accordance with the protocol and local procedures as appropriate. Local Working Instructions will be reviewed at site initiation. Truvada will be stored in a secure, limited access storage area under the specified storage requirements.

The Principal Investigator will ensure that records are maintained showing the receipt, dispensing and destruction of all Truvada. A drug accountability log will be kept to record the identification of the participant to whom the Truvada was given and the date they received drug. The aim will be to provide sufficient to last beyond the next scheduled visit. Any unused Truvada that is returned will also be documented.

It may be necessary for a member of the clinic study team to dispense Truvada at times when a pharmacist is not present. Where this is the case the Principal Investigator will ensure a robust system is in place to capture all required dispensing information.

It may be necessary for drug to be posted to ensure continued supply. When this is the case the Principal Investigator will ensure a robust system is in place to capture the result of the HIV test and urinalysis.

### 5.2.3 DOSE MODIFICATIONS AND INTERRUPTIONS

Truvada must be interrupted if a participant suffers a serious adverse event that could be a drug reaction, or if their renal function is confirmed to be abnormal with no clinical explanation, pending further investigation or specialist referral. Renal function will be assessed using either serum creatinine (in the absence of protein supplements) to estimate glomerular filtration rate, or urinary protein to creatinine ratio according to clinic practice.

Truvada can be reintroduced at the discretion of the clinician, following a discussion with the participant, and the dose can be modified to alternate days or 4 days a week. Should the event recur, and Truvada is the likely cause, drug must be discontinued.

### 5.2.4 TREATMENT DISCONTINUATION

Treatment may be stopped early for any of the following reasons:

- HIV infection
- Unacceptable toxicity or adverse event
- Any change in the participant's sexual behaviour or circumstances that justifies the discontinuation of treatment in the clinician's opinion
- On the recommendation of the Trial Steering Committee/termination of the study by the Sponsor

The participant is free to interrupt or discontinue Truvada. They will be discouraged from doing so if they are continuing to have unprotected anal intercourse.

Even if participants are no longer taking Truvada, every attempt should be made to maintain them in the study. Participants who have confirmed HIV infection do not need further HIV tests but should continue, provided they are willing, to complete the sexual behavioural data and have the STI screens. If a participant is withdrawn from follow-up, refer to [Section 6.6 - Early Stopping of Follow-up](#).

## 5.3 OVERDOSE OF TRIAL MEDICATION

An overdose is defined as

- 2 or more tablets a day for three or more consecutive days OR
- more than 3 tablets in one day

In the event of an overdose, trial treatment will be interrupted and the participant monitored for evidence of renal toxicity until resolution, after which Truvada can be recommenced. The precise frequency of monitoring will be determined by the time that has elapsed since the overdose and whether or not there is any evidence of clinical or laboratory toxicity.

## 5.4 ACCOUNTABILITY & UNUSED DRUGS

The amount of drug given to the participant, and the date, will be recorded on the case record form as well as the amount of drug unused at each study visit. If there is an excess of residual drug or unexpected shortage, an explanation will be sought by the clinic study team. Actual drug dispensed will be compared to expected drug as part of the central monitoring.

All unused trial drug will be collected at the final visit.

## 5.5 COMPLIANCE & ADHERENCE

Information will be provided to all participants on Truvada to ensure comprehension of and compliance with the instructions.

Blood will be collected from up to 50 participants allocated to immediate Truvada in the first instance, and additional sampling will be directed by the Trial Management Group under the guidance of the Trial Steering Committee..

The various measures of adherence will be compared on an aggregated and, where possible an individual level. The adherence results , as well as the barriers and facilitators to adherence identified during the one to one discussions , will be reviewed by the Trial Steering Committee who will advise on the need for further sampling.

## 5.6 NON-TRIAL TREATMENT

### 5.6.1 POST-EXPOSURE PROPHYLAXIS

In the event that a sex act involving anal intercourse is not protected by a condom or Truvada, participants may take post-exposure prophylaxis according to national guidelines.

### 5.6.2 MEDICATIONS THAT ARE NOT RECOMMENDED FOR CONCOMITANT USE

The following medications are not permitted:

- drugs containing emtricitabine or tenofovir disoproxil fumarate including Atripla, Emtriva and Viread
- Adefovir dipoxil
- Lamivudine and other cytidine analogues
- Didanosine
- Cidofovir and other medicinal products that compete for active tubular secretion
- Drugs that reduce renal function

The named medications are not cited in the information sheet as they are not prescribed by General Practitioners, and not available over the counter.

### 5.6.3 MEDICATIONS TO BE USED WITH CAUTION

Co-administration of Truvada with drugs that are eliminated by active tubular secretion may increase concentrations of emtricitabine, tenofovir, or the co-administered drug.

### 5.6.4 TREATMENT AFTER HIV SEROCONVERSION

Participants who seroconvert stop Truvada, and will be managed according to national guidelines. They will continue in follow-up see [Section 6.5.4 - In the event of seroconversion](#)

### 5.6.5 TREATMENT FOR ACTIVE REPLICATION OF THE HEPATITIS B VIRUS

If daily Truvada is required to treat active replication of hepatitis B acquired after enrolment, then this will take precedence over the randomised allocation. Participants may continue in follow-up.

## 6 ASSESSMENTS & FOLLOW-UP PROCEDURES

### 6.1 PRIOR TO ENROLMENT

Potentially eligible men and transgender women (MSM) will be identified during a routine GUM clinic visit at which they report UAI on more than one occasion in the last 90 days, or recognise that they are eligible when they find out about the trial through outreach activities, community organisations and social media. Staff in participating venues who conduct the pre-HIV test counselling will include information on pre-exposure prophylaxis (PrEP) at the same time as post-exposure prophylaxis (PEP) during the enrolment period. Interested men will be able to download the information sheet from the study website or be provided with this (**Appendix I**). A note will be made of the clinic number on a Pre-Screening Log, if given out by clinic staff.

MSM who are interested will have an opportunity to discuss the information sheet with a member of the study team and to ask for any clarification, either during a visit or on the telephone.

The eligibility check prior to enrolment will be done using the GUM clinic records as MSM attending sexual health clinics in the UK are asked about their sexual behaviour and undergo the following investigations as recommended in the Standards for the management of STIs 2013:

- HIV
- Urethral, rectal and pharyngeal chlamydia (nucleic acid amplification test)
- Urethral, rectal and pharyngeal gonorrhoea (nucleic acid amplification test)
- Syphilis RPR/TPHA

Hepatitis B status is checked at the first visit to a clinic. Immunisation against hepatitis B is promoted and delivered in sexual health clinics, and a response confirmed by checking for hepatitis B surface antibodies.

If there are no reasons for exclusion based on the available information, and the subject wishes to proceed to a trial visit, an appointment will be made and they will be asked to make a note of their sexual behaviour (number of partners and number of episodes of UAI).

### 6.2 TRIAL SPECIFIC ASSESSMENTS & PROCEDURES

#### 6.2.1 ENROLMENT VISIT (MONTH 0)

##### 6.2.1.A Pre-randomisation procedures

The study staff will ascertain that the information sheet has been fully understood and obtain written informed consent.

There will be a clinic interview, during which baseline demographic, clinical and behavioural data relevant to the eligibility criteria in Section 3.1 and 3.2 will be collected onto a case record form. The behavioural and lifestyle information provided by the individual and available in the clinic record will inform the development of a personalised plan for reducing their risk. A screen for sexually transmitted infections and point of care test for HIV will be performed if these are indicated, according to routine clinic practice. A specimen of urine will be collected for analysis in clinic.

The study staff will explain how to complete the diary and behavioural questionnaires and make sure the questions are clear. Participants will then be asked to complete the short (last 30 days) and a

long (last 90 days, lifestyle and well-being) behavioural questionnaires, in private, and to place these in a sealed envelope and hand them in to study staff in the clinic, to be sent on to MRC CTU for data entry.

#### **6.2.1.B Randomisation procedures**

Randomisation should be performed on the day of the enrolment visit while the participant is present in the clinic, and after the eligibility check described above. If there are eligibility queries, these should be clarified with a member of staff at MRC CTU before randomisation.

Randomisation will be performed using a computer-generated randomisation list. Clinic staff will be able to go through the randomisation checks online, or in circumstances when this is not available by phone/fax to the MRC CTU. The participant's trial number, allocation and the date of randomisation will be entered into the Trial Register at the clinic and at the MRC CTU.

#### **6.2.1.C Post-randomisation procedures**

All participants will receive support to adhere to the agreed plan to manage their personal risk, and counselling about the importance of adhering to the agreed schedule of visits. All participants will be provided with sufficient monthly questionnaires to last until the next visit, and stamped addressed envelopes if they have selected to complete these manually. A diary will also be provided to record acts of anal intercourse and condom use, different partners, and pill taking when applicable.

A blood sample to confirm HIV status using an antigen/antibody assay should be collected and processed according to the clinic routine. In the event of an indeterminate or positive result, the participant will be recalled for further investigation.

For participants starting Truvada IMMEDIATELY, at month 12 or earlier, the clinician and participant will go through the instructions for use of with Truvada (see [Sections 5.2.1 Treatment Schedule](#)). They will be issued with 1 bottle, containing 30 tablets, and the next clinic appointment will be made before they could run out of drug. They will be asked to tick the days they take drug on the diary. The clinician will ensure that the participant understands that

- it takes two weeks before drug has reached a steady level in the tissues and that the drug may be less effective during this period
- their risk may not be reduced if they have missed 3 or more tablets in the week before unprotected anal intercourse
- starting or restarting Truvada when they have caught HIV increases the chance of resistance to Truvada

The clinician will use this information to advise participants on the circumstances in which they should consider post-exposure prophylaxis.

A blood sample will be collected to determine renal function, using serum creatinine to estimate the glomerular filtration rate.

Following a recommendation from the Trial Steering Committee on 9th October 2014, participants who are still in the first 12 months of the deferred period are to be recalled and offered Truvada. They will be provided with a supplementary PIS - New Information about treatment being studied (Appendix X) and asked to sign the accompanying consent (Appendix XI), after which the clinician and participant will go through the instructions as described in Sections 5.2.1 Treatment Schedule and 6.2.1.C Post-randomisation procedures above.

#### **6.2.2 FOLLOW-UP AFTER ONE MONTH ON TRUVADA:**

This assessment, which can take place in the clinic or by telephone, is required for

- **participants randomised to IMMEDIATE Truvada** at month 1
- **participants randomised to DEFERRED Truvada** at month 13 (or earlier)

There will be an interview to see if the participant has experienced any side-effects sufficient to interrupt Truvada, and how they are managing to fit the daily pill into their routine schedule. Urine will be collected for analysis if they attend a study clinic. In the presence of 1 + of protein in the urine of a participant who is taking Truvada, and the absence of nitrites which makes a urinary tract infection less likely, a blood or urine sample will be collected to check renal function according to clinic routine.

A short questionnaire will be completed either during the study clinic visit or at the time of drug collection if the visit is conducted on the telephone, and placed in a sealed envelope to be sent to MRC CTU. If participants prefer to enter their data directly into the participant database they may do so.

A blood specimen may be collected for the analysis of drug levels.

Unused pills will be recorded on the case record form, and checked directly if the participant brought these to clinic. Sufficient drug will be dispensed to last beyond the next appointment approximately two months later. If the study assessment was conducted on the telephone, the participant will need to attend to collect their drugs.

### 6.2.3 QUARTERLY CLINIC FOLLOW-UP (MONTHS 3, 6, 9, 12, 15, 18, 21, 24, AND 3 MONTHLY TO EXIT)

Three monthly checks of HIV status and an STI screen are required for **all participants**. These visits may be conducted on the telephone supported by data collected in another clinic.

There will be contact with the study team to review the participant's personal risk reduction plan and determine whether additional support is required. A short questionnaire will be completed during the study clinic visit, or at the time of drug collection if the contact takes place on the telephone or via NHS email, and placed in a sealed envelope to be sent to MRC CTU.

During periods in which the participant is taking Truvada, the clinician will ascertain whether there have been any side-effects sufficient to lead to interruption of drug, and any serious adverse events.

During this visit the following investigations will be performed according to clinic routine:

- HIV test
- Urethral, rectal and pharyngeal swabs for *Chlamydia trachomatis* and *Neisseria gonorrhoea*
- serology for syphilis and hepatitis C when indicated
- Urinalysis

If these tests have been collected since the previous study visit, either at the enrolling clinic or another clinic, the results already available will be used, and tests only collected on the day of the visit if clinically indicated.

In the presence of 1 + of protein in the urine of a participant who is taking Truvada, and the absence of nitrites which makes a urinary tract infection less likely, a blood or urine sample will be collected to check renal function according to clinic routine.

A blood specimen may be collected for the analysis of drug levels.

Unused pills will be recorded on the case record form, and checked directly if the participant brought these to clinic. Sufficient drug will be dispensed to last beyond the next appointment approximately

three months later. Up to six months can be dispensed provided the participant is able to obtain a HIV test through another clinic or self-sampling and communicate the result to the study team.

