## TRIAL SCHEMA

**Figure 1. Trial Entry, Randomisation and Treatment**

## TRIAL ASSESSMENT SCHEDULE

X means mandatory, (X) means if indicated or if willing

	Prior to Enrolment	Day 0 (Baseline)	Monthly between visits	First month on PrEP	Quarterly 3,6,9,15,18,21 then 3 monthly	Annual & Exit 12,24,(36),Exit
Informed consent		X			(X)	(X)
Eligibility check	X a					
Inclusion/exclusion criteria		X				
Randomisation		X				
Baseline HIV/STI/demographics		X				
Visit/Contact case record form				X	X	X
SAE assessment				X	X	X
Dispensing and Pill count		X b		X b	X b	X b
Daily diary c		(X ←				→ X)
Short Behaviour Questionnaire c		X	(X)	(X)	X	X
Long Behaviour & Lifestyle Questionnaire c		X				X
Acceptability Questionnaire						X
In depth interview (IDI) d		X		X	X	X
HIV test	X a	X			X	X
STI screen	X a	(X)		(X)	X f	X f
Urinalysis for Protein		X		(X)	X	X
Serum Creatinine		Immediate		(X) e	(X) e	X
PK sample collection d				(X)	(X)	(X)

a Eligibility will be determined on the basis of routine data such as sexual behaviour, HIV and hepatitis B status, STI screening

b Immediate group months 0-exit; deferred group months 12 or earlier subject to reconsent (see Section 6.6 –exit)

c The questionnaires will be completed by participants at visits and posted to MRC CTU, and may be entered directly online between visits

d The IDIs and PK samples will be in a selected subset in the first instance, and thereafter on the recommendation of the Trial Steering Committee

e At these visits clinics will monitor renal function according to their routine practice which will be serum creatinine or urinary protein:creatinine ratio

f urine/urethral swab and rectal swab for neisseria gonorrhoea and chlamydia trachomatis and blood for syphilis, and for hepatitis C when indicated except at exit when collected in all participants

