## 6.5 OTHER ASSESSMENTS

### 6.5.1 SELF-REPORTED BEHAVIOUR

Self-reported sexual and adherence behaviours will be collected in the daily diary and short and long questionnaires.

The **diary** will be a simple record for noting acts of anal intercourse, whether or not a condom was used throughout, and whether or not a pill was taken each day. The facility to enter this information directly into a database held at MRC CTU will be available for participants that have access to the web, and wish to do this. Data will be identifiable to CTU staff by trial number and date of birth only. Participants that record the diary manually will be asked to post these to MRC CTU or to bring them to their next clinic visit.

Participants will be asked to summarise their sexual and adherence behaviours in the **short (last 30 days) questionnaire** when they attend the study visit or collect drug, and to place these in a sealed envelope for forwarding on to MRC CTU. For participants that are using the participant database, the questionnaires can be completed each month online at home or in clinic..

A **long (last 90 days) questionnaire** that includes lifestyle and well-being questions as well as sexual behaviour will be completed during the clinic visits at baseline, when starting Truvada if earlier than month 12, and at annual visits in private.

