#### 9.2.2 OTHER OUTCOME MEASURES

- HIV infections acquired between trial entry and 12 months, and between 12 and 24 months
- Safety
  - Serious Adverse Reactions attributable to Truvada
  - Any adverse event leading to interruption or discontinuation of Truvada
  - Renal function estimated using serum creatinine at 12 months
  - Presence of viral resistance mutations likely to have been selected by Truvada (K65R, M184V) in participants who acquire HIV infection.
- Adherence:
  - Proportion of doses taken estimated from self-report
  - Proportion of days covered according to dispensing records for the daily schedule
  - Presence of drug as expected in a subset of selected participants
- Risk Compensation:
  - Number of sexual partners with whom had UAI, UIAI and URAI (unprotected defined as without a condom) between trial entry and month 12 and month 12 to month 24
  - Number of acts of AI, protected and unprotected by a condom, between trial entry and month 12 and month 12 to 24
  - Proportion of acts of AI protected by either condom, PrEP or both between trial entry and month 12 and month 12 to 24
  - Sexually transmitted infection (STIs) acquired between trial entry and month 12
  - Sexually transmitted infection (STIs) acquired between month 12 and month 24
- Other:
  - Facilitators and barriers to adherence to a personal risk reduction plan in a subset of selected participants

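### At telephone or email contacts the short questionnaire is prompted only by drug collection, so missing self-reported adherence and 30-day behaviour data may depend on whether a man is taking Truvada

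*Protocol*

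**What the plan says.** Protocol section 6.2.3 opens remote quarterly contacts to all participants: "These visits may be conducted on the telephone supported by data collected in another clinic". The short questionnaire is then completed in clinic, "or at the time of drug collection if the contact takes place on the telephone or via NHS email". Section 6.5.1 states the same rule in general terms: men fill it in "when they attend the study visit or collect drug".

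The Trial Assessment Schedule puts an unbracketed X against the short questionnaire in the quarterly column. Its key reads "X means mandatory, (X) means if indicated or if willing", and nothing limits the entry to men on drug.

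Other routes exist. Section 6.5.1 adds: "For participants that are using the participant database, the questionnaires can be completed each month online at home or in clinic". Footnote c of the schedule says the questionnaires are posted to the trials unit and "may be entered directly online between visits". Section 6.2.1.C supplies monthly forms at enrolment, with "stamped addressed envelopes if they have selected to complete these manually".

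The form records perceived adherence and missed doses (section 6.5.3) and sexual behaviour over the last 30 days (sections 6.5.1 and 6.5.2). It feeds the outcome "Proportion of doses taken estimated from self-report" in section 9.2.2 and the between-group behaviour comparison in section 9.5.

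**The concern.** The form is required of everyone, but at a remote contact its stated completion point is an event that some participants do not have. Section 5.2.4 asks sites to keep men in the study after they stop Truvada, and these men collect nothing. Nor do men who decline the offer, or deferred men before they start (section 5.2).

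If the stated rule is followed, whether a man is prompted for the form at a remote contact depends on whether he is taking the drug. That would matter in two places. Self-reported adherence would tend to come from men still collecting tablets. The behaviour comparison would use data whose missingness may be related to PrEP use, which is the exposure whose effect on behaviour the trial wants to learn about.

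**Working it through.** The plan states no figure on this point, so there is none to reproduce. The check has two parts.

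**1. The text, group by group, at a remote quarterly contact**

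| Group | Form mandatory? | Prompted at drug collection? | Other routes |
|---|---|---|---|
| On Truvada, collecting in person | Yes | Yes | Online, post |
| On Truvada, drug posted (5.2.2) or holding up to six months' supply (6.2.3) | Yes | Not at every contact | Online, post |
| Stopped or interrupted, kept in follow-up (5.2.4) | Yes | No | Online, post |
| Declined the offer | Yes | No | Online, post |
| Deferred, not yet started (5.2) | Yes | No | Online, post |

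The split is not cleanly on-drug against off-drug, because some men on drug also lack a collection event. But no man off drug has one.

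Section 6.2.2, on the one-month contact, uses the same drug-collection rule but adds that participants may enter data directly into the database. Section 6.2.3 omits that sentence. The version 1.3 entry in section 16 explains the rule: completion had been very low, so forms would be requested in clinic or when drug is collected. At remote contacts that remedy reaches only men who collect drug.

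**2. Possible size for self-reported adherence**

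None of these inputs is in the documents; all are assumed:

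- m, mean adherence among men on drug: 80% to 90%
- s, share of men off drug, counted as 0% adherence: 5% to 20%
- r, share of off-drug men's contacts that are remote: 10% to 50%
- o, share of those remote contacts captured online: 0, one half, or all

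All other questionnaires are taken as returned, and off-drug men are taken to belong in the denominator.

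True mean = m(1 − s).

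Observed mean = m(1 − s) / [(1 − s) + s(1 − r(1 − o))].

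| m | s | r | o | True | Observed | Overstatement (points) |
|---|---|---|---|---|---|---|
| 80% | 5% | 10% | 0 | 76.0% | 0.76/0.995 = 76.4% | 0.4 |
| 90% | 10% | 30% | 0 | 81.0% | 0.81/0.97 = 83.5% | 2.5 |
| 90% | 20% | 50% | 0 | 72.0% | 0.72/0.90 = 80.0% | 8.0 |
| 80% | 5% | 10% | 0.5 | 76.0% | 0.76/0.9975 = 76.2% | 0.2 |
| 90% | 20% | 50% | 0.5 | 72.0% | 0.72/0.95 = 75.8% | 3.8 |
| any | any | any | 1 | m(1 − s) | m(1 − s) | 0 |

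So the range is 0.4 to 8.0 points with no online capture and 0.2 to 3.8 with half captured. Postal return would act in the same way as online capture.

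An extreme case (m = 90%, s = 20%, every off-drug contact remote, no online capture) gives 90.0% observed against 72.0% true, or 18.0 points. It needs every off-drug man to be missed at every contact.

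If adherence is defined only over time on drug, off-drug men are not in the denominator and this mechanism adds nothing.

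No comparable figure is offered for sexual behaviour. The documents give no basis for how behaviour differs between men who return the form and men who do not, so even the direction is open.

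**The case against.** The strongest reply is that this is a gap in wording with little consequence.

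- **Other routes exist.** A reader might infer that off-drug men cannot submit the form remotely, and so vanish from the self-reported data. The documents do not support that. Online entry and paper with prepaid return are both provided, clinic visits still capture these men, and section 6.2.4 takes the long questionnaire from all participants at annual and exit visits. What survives is that these routes are voluntary and unprompted, and completion under them was already poor.
- **The deferred arm.** A reader might infer a year of arm-related missingness. The drug-collection rule dates from version 1.3 of 14 October 2014. Under that same version deferred men are recalled and offered Truvada (section 6.2.1.C), with the aim of seeing them before the end of November 2014 (section 1.4). For men seen as planned, the exposed period is at most about seven weeks (14 October to 30 November, 47 days). This objection largely stands. The lasting gap concerns men who stop, interrupt or decline, or who are not reached.
- **Adherence has other measures.** The diary also feeds self-report, and dispensing records, drug levels and MEMS caps do not use this form (sections 6.5.3 and 9.2.2). This stands for those outcomes. But section 5.5 plans to compare the measures, individually where possible, and that comparison is weaker where self-report is missing for men who stopped.
- **Behaviour has other measures.** Annual questionnaires and quarterly STI screens remain, and the version 1.3 entry in section 16 relies on them. This limits the damage without restoring the 30-day data.
- **The denominator belongs to the SAP.** Agreed. The SAP is not at hand, and whether stopped periods count as zero doses is for it to settle. That is why any bias here is conditional.

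**Conclusion.** The point holds in a limited form. Sections 6.2.3 and 6.5.1 tie the prompted remote completion of a form that is mandatory for all to an event that men off Truvada do not have. Missingness of short-form adherence and 30-day behaviour data may therefore depend on drug use.

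A reader might go further and conclude that self-reported adherence is overstated, even by tens of points. The documents do not show that. They give no share of remote contacts, no share of men off drug and no online or postal capture rate, and they leave the denominator open. The range of 0.4 to 8.0 points (0.2 to 3.8 with half captured online) rests wholly on the assumed inputs above. It falls to zero with full capture, or if adherence is defined only over time on drug. The effect on the behaviour comparison is possible but cannot be sized or signed.

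This does not touch the main outcomes of accrual and retention, or the HIV endpoint. It is a modest weakness in data collection that is cheap to remove.

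**What to change.** In sections 6.2.3 and 6.5.1, state that at every telephone or email contact the short questionnaire is requested at the time of the contact, through the existing online database or a posted form, whether or not drug is collected. Carry the online-entry sentence of section 6.2.2 into section 6.2.3 so that the two agree. Have the contact case record form note whether the participant is currently taking Truvada. Report short-questionnaire completion by arm and by on/off-drug status, so that any remaining imbalance can be seen. Leave the counting of stopped periods to the SAP.

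The cost is a wording change and, at most, one item on the contact form; the database and the postal route already exist. Some remote forms will still not come back, but the request will no longer depend on collecting drug.
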